9.11 Pharmacokinetic/Pharmacodynamic Analyses

A Population Pharmacokinetic Analysis Plan will be prepared prior to the population PK analyses. This plan will describe the underlying hypotheses, the population PK analysis set, and the statistical methods to be used.

9.12 Pharmacogenomic Analyses

A separate pharmacogenomic analysis plan will be prepared prior to unblinding of the pharmacogenomic data and the subsequent exploratory pharmacogenomic analysis. ^{CCI}

9.13 Other Outcomes

The change from baseline variables for the EQ-5D index utility score and VAS scores, SF-36 Physical Component and Mental Component summary T scores, and the 8 SF-36 domain T scores will each be analyzed as a continuous variable by study visit using an MMRM model similar to the ones described above for the key secondary variables. (The Physical Component and Mental Component summary scores and reliability consistency index scores will be included in the derived datasets, but analyses for these variables will not be presented in the CSR; they may be provided in the future in a separate report.)

For the following endpoints (corresponding to the analysis method for the key secondary endpoints), subgroup/responder analyses by MCI event status (ie, subject had confirmed a MCI due to AD event during the study, subject did not have confirmed MCI due to AD event during the study) will be done (using the corresponding measurements at the time of the MCI due to AD

event or using the last non-missing measurements for subject who did not have an MCI due to AD event during the study:

- Change in HRQoL (European Quality of life scale [Euro-Qol EQ-5D] health utility and VAS scores, and Short Form-36 [SF-36] Mental and Physical component scores).

Responder analyses involve subgroups which are defined using post-baseline data and so need to be interpreted cautiously. Analysis results for subgroups containing less than 20% of the total subjects in the primary efficacy analysis population should be interpreted especially cautiously. The treatment groups will be compared within each subgroup. Additional exploratory analyses examining subgroup effect and treatment-by-subgroup interaction may be performed.

Data will be collected to allow evaluation of the impact of pioglitazone on health care resource utilization (RU) in individuals at high risk of developing MCI due to AD, to be used in future pharmacoeconomic evaluation of pioglitazone. (These analyses will not be presented in the CSR, but may be provided in the future in a separate report.)

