9.1.17 Order of Assessments

Sites should make every attempt to adhere to the assessment schedule in [Table 9.c](#). Should an interruption occur during the visit, the subject, and/or project partner, may return to the site within 2 weeks to complete the assessments. During the Baseline Visit only, sites may elect to administer the CDR prior to the Cognitive Test Battery to evaluate subject eligibility. The ADCS-CGIC-MCI may be administered in parallel with, or before other testing, as long as the tester is blinded to any adverse events or other test results.

Table 9.c Order of Assessments

Cognitive Test/Questionnaire	Visit	Assessor
MMSE	Visit 1, Visit 2, every 6 and 12 month visit after randomization, EoS/EW Visit	Certified tester
Cognitive Test Battery (completed in this order)	Visit 2, every 6 and 12 month visit after randomization, Unscheduled Visit, EoS/EW Visit	Certified tester
1. CVLT-II: Trials 1-5; Short delay recall trials.		
2. BVMT-R: Learning trials 1-3.		
3. Digit Span Forward.		
4. Digit Span Backward.		
5. Trails A.		
6. Trails B.		
7. CVLT-II: Delayed recall (15-30 minutes should have elapsed from end of short recall and long-delay).		
8. CVLT-II: Recognition trial.		
9. BVMT-R: Delayed recall (15-30 minutes should have elapsed from Trial 3 to delay)		
10. BVMT-R: Recognition trial.		
11. BVMT-R: Copy trial.		
12. MINT.		
13. Semantic fluency (animals).		
14. Lexical fluency.		
15. CDT.		
GDS	Visit 2, every 6 and 12 month visit after randomization, EoS/EW Visit	Study Subject

Footnotes are on last table page.

CONFIDENTIAL

Table 9.c Order of Assessments (continued)

Cognitive Test/Questionnaire	Visit	Assessor
ADCS-MCFSI	Visit 2, every 6 and 12 month visit after randomization, EoS/EW Visit	Study Subject
EQ-5D	Visit 2, Unscheduled Visit, EoS/EW Visit	Study Subject
SF-36	Visit 2, Unscheduled Visit, EoS/EW Visit	Study Subject
IQCODE	Visit 2, every 6 and 12 month visit after randomization, EoS/EW Visit	Project Partner
ADCS ADL-PI	Visit 2, every 6 and 12 month visit after randomization, EoS/EW Visit	Trained Tester
NPI-Q	Visit 2, Unscheduled Visit, EoS/EW Visit	Project Partner
ADCS-RUI	Visit 2, every 6 and 12 month visit after randomization, Unscheduled Visit, EoS/EW Visit	Trained tester
CDR (a)	Visit 2, Unscheduled Visit, EoS/EW Visit	Investigator/ Sub-Investigator (b)
ADCS-CGIC-MCI (c)	Visit 2, every 6 and 12 month visit after randomization, Unscheduled Visit, EoS/EW Visit	Trained tester (b)

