Appendix A Schedule of Study Procedures (continued)

	Screening Visit 1	Base-line Visit 2	Random-ization Visit 3	Double-Blind Treatment Repeated yearly				Unscheduled - CMFV (q) (v)	EoS / EW Visit (b) (j)	Follow-up Visit (c)
				3 (a)	6	9 (a)	12			
Study Month:	-4	-1	0 (Day 0)	3 (a)	6	9 (a)	12			EoS/EW+0.5
Visit Window (t):	Max Day -125	Max Day -35		±2 weeks	±2 weeks	±2 weeks	±2 weeks	Within approx. 30 days of trigger		
Efficacy (continued)										
GDS		X			X		X		X(u)	
ADCS-MCFSI		X			X		X		X(u)	
EQ-5D		X						X	X(u)	
SF-36		X						X	X(u)	
IQCODE		X			X		X		X(u)	
ADCS ADL-PI		X			X		X		X(u)	
NPI-Q		X						X	X(u)	
ADCS-RUI		X			X		X	X	X(u)	
CDR		X						X	X(u)	
ADCS-CGIC- MCI		X			X		X	X (u)	X(u)	

Footnotes are on the following page.

Excl=exclusion, Incl=inclusion.

- (a) Telephone contact (should be every 3 months between the semi-annual clinic visits for the life of the study).
- (b) EoS/EW Visit is an ad hoc visit that, for study completion, would take place as soon as possible after a regularly scheduled Study Visit, either after the CIAC has confirmed that the subject has reached the MCI due to AD primary endpoint event (or any other irreversible cognitive impairment or dementia) or after a subject has withdrawn prematurely from the study. In cases where the endpoint has been reached, the efficacy assessments will not need to be captured at this Visit.
- (c) Subjects will have a safety follow-up call 2 weeks after completion or withdrawal. Subjects who withdraw their consent should still be contacted for a safety follow-up call, but the contact should only be recorded in the medical records (and not in the [e]CRF), according to data protection regulations.
- (d) footnote deleted
- (e) Please refer to Section 10.2.1.3.
- (f) As part of the comprehensive medical follow-up evaluation to rule out other causes of dementia and confirm the clinical diagnosis of MCI due to AD (See section 6.2.4). An MRI scan is not required to be performed if a study related MRI scan was collected within 6 months of the CMFV. For subjects who have contraindications for the MRI procedure (such as unremovable ferromagnetic dental work, cardiac pacemakers, etc) a CT scan can be done instead.
- (g) DNA sample expected to be collected at this visit, but if necessary, may be collected at any visit after randomization.
- (h) Sites should make every attempt complete the cognitive test battery in the order of outlined in Section 9.1.17.

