- (i) Cognitive Battery is completed at an Unscheduled Visit or EoS/EW Visit if the visit occurs greater than 3 months after the previous regularly scheduled visit.
- (j) Subjects who discontinue study medication prematurely should be contacted by the study site every 6 months until the conclusion of the study via telephone to assess the general well being of the subject as well as to obtain any changes in medications related to cognitive health. In the event the subject is not able to be reached, the subject's project partner or primary care physician can be contacted to obtain this information.
- (k) female subjects only.
- (l) Family history is captured at the first 6 month visit during year 1 of the study.
- (m) Please refer to Table 9.a and lab manual for detailed test schedule.
- (n) RNA sample to be collected at Day 0, Month 12 of Year 1, Year 2, Year 3, Year 4 and EoS.
- (o) Greater detail is given below. Note: If subject has been off drug for 3 or more days prior to Unscheduled CMFV, or EoS/EW Visit, the PK samples should not be collected.
- (p) A subject's age will be collected at these post-Baseline study Visits only in countries that do not allow collection of a subject's date of birth.
- (q) Procedures for Unscheduled visits for CMFV includes the assessments marked, and should only be conducted after appropriate criteria are met as described in Section 6.2.4. Unscheduled visits for other concerns, including safety, the investigator is expected to conduct whatever assessments are necessary.
- (r) If sites prefer to split the ICF process at Visit 1 and Visit 2 into a screening informed consent and study entry informed consent and have IEC/RIB approval to do so, this is permitted.
- (s) ADCS-RUI should be administered every 6 months.
- (t) Visit Window also applies to Project Partner assessments.
- (u) These assessments only need to be administered at the applicable visit if it occurs greater than 3 months from the last administration of the particular assessment.
- (v) At the Investigator's discretion, CMFV assessments may be conducted at the routine Month 6 or Month 12 Visit in situations where the CMFV conducted as an outcome of the previous scheduled office visit resulted in an MCI due to AD diagnosis. Refer to Section 6.2.4 for further detail.

CONFIDENTIAL

Schedule for Pharmacokinetic Sample Collection

Group	Dosing Time (approximate)	Sample Collection(a)			
		Pre-Dose	Sample Collection Time Post-Dose		

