9.9.6 Analysis of Key Secondary Variables

The change from baseline in cognitive battery composite score will be analyzed as a continuous variable by study visit using MMRM (mixed model for repeated measures) analysis of covariance with treatment, gender, center, visit, and treatment-by-visit interaction as fixed, categorical effects and education, age, baseline composite score, and baseline composite score-by-visit as continuous, fixed covariates. The effect at each time point for each treatment is allowed to vary freely, and an unstructured covariance matrix will be used to model the within-subject errors. The Kenward-Roger approximation will be used to estimate denominator degrees of freedom. Based on a Missing at Random (MAR), this analysis will be performed using observed case data only.

The SAS code for the MMRM analysis will be as follows:

```
Proc mixed data=all;
```

- class visit treat center gender subject;
- model Change = Baseline Baseline*visit treat center gender education age visit visit*treat /solution ddfm=KenwardRoger;
- repeated visit/subject=subject type=UN;
- lsmeans visit*treat / cl pdiff.

In the above model, Baseline is the baseline value and Change is the change from baseline value.

Similarly, the change from baseline in ADCS ADL-PI ADL total score will be analyzed as a continuous variable by study visit using MMRM, where the ADCS ADL-PI ADL total score Baseline, gender, education, and age will be used as the covariate adjustments in the MMRM.

Key secondary endpoints will be analyzed (including reporting mean differences, CIs, and p-values) using the FAS subjects in the primary efficacy population (high-risk, non-Hispanic/Latino subjects) using a 0.01 significance level.

Although change-from-baseline endpoints will be assessed at all visits, the primary time frame for purposes of efficacy analysis is the change from baseline to Month 48 (Year 4).

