The change from baseline variables for the CVLT-II test (CVLT_T1, CVLT_T2, CVLT_T3, CVLT_T4, CVLT_T5, CVLT_TOT, CVLT_TB, CVLTSDEL, CVLTLDEL, CVLTINTR, CVLT_REP, CVLTHITS, and CVLT_FP) will each be analyzed as a continuous variable by study visit using an MMRM model similar to the ones described above for the key secondary variables.

The change from baseline variables for the cognitive battery domain scores (memory, executive function, language, and attention) will each be analyzed as a continuous variable by study visit using an MMRM model similar to the ones described above for the key secondary variables.

The change from baseline variables for GDS Total score, ADCS MCFSI total score, IQCODE Overall mean score, and ADCS ADL-PI Physical Function total score will each be analyzed as a continuous variable by study visit using an MMRM model similar to the ones described above for the key secondary variables.

The ADCS-CGIC-MCI total, cognition, behavior, and functional ability scores will each be analyzed as continuous variables by study visit using a MMRM models similar to the ones described above for the key secondary variables (using the appropriate corresponding ADCS-CGIC-MCI baseline score). In addition, each of these 4 ADCS-CGIC-MCI variables will be analyzed at the last visit using the Cochran-Mantel-Haenszel test and stratifying by center.

The MMSE total score is scheduled to be collected at 6-month visits and EoS/EW. Summary statistics will be used to present MMSE total score and change from baseline in MMSE total score at EoS/EW.

The CDR and NPI-Q are scheduled to be collected at baseline and EoS/EW. The CDR Global Score and domain scores will be presented using shift tables from baseline to EoS/EW. Summary statistics will be used to present CDR-SB and change from baseline in CDR-SB at EoS/EW. In addition, each of the 6 CDR domain scores at Baseline and at each time point when MCI due to AD was diagnosed will be included in the listings.

For each of the NPI-Q variables Total Severity Score and Caregiver Distress Score, the change from baseline in NPI-Q from baseline to EoS/EW will be analyzed using an ANCOVA model analogous to the model for the key secondary endpoints. The following SAS code will be used for the ANCOVA analysis:

- Proc mixed data=all;
- class treat center gender;

- model Change = Baseline treat center gender education age;
- lsmeans treat / cl pdiff;

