MRIs will be done as part of the comprehensive medical follow-up evaluation to rule out other causes of dementia and confirm the clinical diagnosis of MCI due to AD (see Section 6.2.4 of the protocol). For subjects who have contraindications for the MRI procedure (such as unremovable ferromagnetic dental work, cardiac pacemakers, etc) a CT scan can be done instead. The possible categories for the interpretation results are: Within Normal Limits; Abnormal, Not Clinically Significant; and Abnormal, Clinically Significant. The last available MRI/CT scan interpretation results for each subject will be summarized by treatment group, and all MRI/CT scan interpretation results will be presented in the listings.

Except for time-to-event analyses and the summary of MRI interpretation results, unscheduled visit values will be excluded from the summaries and analyses but will be included in the end-of-text CSR listings.

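### SAP 9.13 plans a by-visit MMRM for EQ-5D and SF-36, but the protocol collects neither at routine post-baseline visits

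*SAP*

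**What the plan says.** **Analysis.** SAP 9.13 states that the change-from-baseline variables for the EQ-5D index and VAS, the SF-36 physical and mental component T scores and the eight SF-36 domain T scores are to "each be analyzed as a continuous variable by study visit using an MMRM model similar to the ones described above"; the model meant is the key secondary one. In that model (SAP 9.9.6) treatment effects vary freely by visit, "an unstructured covariance matrix will be used to model the within-subject errors", and denominator degrees of freedom follow Kenward-Roger. Month 48 is named there as the primary time frame for change-from-baseline endpoints.

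**Collection.** Protocol Table 9.c gives the same entry for EQ-5D and SF-36: "Visit 2, Unscheduled Visit, EoS/EW Visit". Appendix A agrees; the Month 6 and Month 12 cells for both are blank.

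**Which values count.** SAP 9.9.9 says: "Except for time-to-event analyses and the summary of MRI interpretation results, unscheduled visit values will be excluded from the summaries and analyses". Appendix A then thins the EoS/EW value. Footnote (b) says "In cases where the endpoint has been reached, the efficacy assessments will not need to be captured at this Visit", and EQ-5D and SF-36 are listed there under efficacy. Footnote (u) says "These assessments only need to be administered at the applicable visit if it occurs greater than 3 months from the last administration".

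**The comparable instrument.** NPI-Q has the same visit entry in Table 9.c. For it, SAP 9.9.9 says "the change from baseline in NPI-Q from baseline to EoS/EW will be analyzed using an ANCOVA model". SAP Table 9.a, footnote (c), marks CDR and NPI-Q as sparsely collected. It does not mention EQ-5D or SF-36, which therefore fall under the six-monthly windows.

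**The concern.** An MMRM earns its place when the same subject is measured at several visits: the within-subject correlation lets earlier values inform later ones. EQ-5D and SF-36 have no routine post-baseline series. A by-visit table would still show a treatment difference at each six-month window, and a reader would take each as the effect in the randomized population at that visit. It would in fact describe whichever subjects supplied a value in that window, a group defined by exit or by a cognitive trigger.

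**Working it through.** The documents give no sample size, power or alpha for EQ-5D or SF-36, so there is no plan figure to reproduce. The check has three parts.

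**1. Values per subject.** Collection is at baseline, CMFV and EoS/EW. Applying the 9.9.9 exclusion removes the CMFV value and leaves at most one post-baseline value, at EoS/EW. Footnotes (b) and (u) can remove that one too.

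**2. What the covariance model can estimate.** SAP Table 9.a has 11 post-baseline windows for these variables: Months 6, 12, 18, 24, 30, 36, 42, 48, 54, 60 and 66/Final.

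- Unstructured parameters: 11 × 12 / 2 = 66.
- Variances: 11. Covariances: 11 × 10 / 2 = 55.
- A subject seen once, in window k, contributes a likelihood term containing only the mean and variance for window k. No covariance enters.
- Numerically, the information matrix for the 66 parameters, with one value per subject spread over all 11 windows, has rank 11.

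So the 55 covariances are unidentified. The window means and variances remain estimable where a window holds enough subjects, but no window informs another.

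**3. Who supplies each window.** Protocol 9.3.6 expects the final visit four years after enrollment ends, so no administrative completion is expected before about day 4 × 365.25 = 1,461. The Month 42 window ends on day 1,369. Up to that point EoS/EW values come mostly from withdrawals, with some study-ending diagnoses.

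The Month 48 window covers days 1370 to 1551. For an illustration I assumed uniform enrollment over 1 to 2 years, a final visit 4 years after enrollment ends, exponential dropout of 8% to 12% per year, an average 5-year event rate of 12% (midway between the planned 15% and 9%) and no EoS value for converters. Only the 12% dropout, the 15% and 9% rates and the four-year timing come from the documents.

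- Still in the study at day 1370, with 12% dropout: rates −ln(0.88) = 0.128 and −ln(0.88)/5 = 0.0256 per year; exp(−0.1534 × 1370/365.25) = 0.56. With 8% dropout: exp(−0.1090 × 3.751) = 0.66.
- Supplying a value in the Month 48 window (simulated): from 9.9%, or 232 of 2,346 (two-year enrollment, 12% dropout), to 18.3%, or 430 of 2,346 (one-year enrollment, 8% dropout).
- Dropouts among those suppliers: 14% to 34%. The rest are administrative completers.

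Under these assumptions 56% to 66% of subjects are still under observation at day 1370, yet a Month 48 contrast would use only 10% to 18% of those randomized.

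**Other readings of the SAP.** If CMFV values are admitted, the interim windows hold mainly cognitively triggered subjects, and the covariances rest on those with more than one value, chiefly the repeatedly triggered. If EoS/EW is its own time point, there is no Month 48 value and the model reduces to a single-time-point ANCOVA. Neither reading gives a by-visit comparison of the randomized groups.

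**The case against.** The best defense is that the text leaves room. SAP 9.13 asks only for a similar model. The exclusion of unscheduled values is printed in 9.9.9, not 9.13, and the second paragraph of 9.13 uses quality-of-life values from the time of the MCI event, which for converters would ordinarily come from a CMFV. Protocol 6.2.4 lets a CMFV share a routine visit date after an earlier CMFV diagnosis of MCI due to AD. SAP 9.9.9 summarizes EoS/EW alongside the visits, and it ties the by-visit MMRM to continuous endpoints measured at more than one scheduled visit. This stands in part: the limit of one value per subject and the Month 48 reading depend on how these sections are joined. It does not rescue the plan, because 9.13 names both the MMRM and the by-visit analysis, and each reading leads to one of the outcomes above. The shared-visit allowance reaches only a selected, near-endpoint group.

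A reader might infer more than the documents support:

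- *That the model will fail to converge.* Not shown. The visit contrasts remain estimable; the unidentified covariances may trouble the Kenward-Roger step, but no fit was shown to fail.
- *That the missing-at-random assumption is broken.* Values absent for everyone under the schedule are missing by design, and absence through administrative study end is not outcome-driven. Only dropout and event-related exit raise that question.
- *That Month 48 compares only dropouts.* The expected study-end timing puts some administrative completers in that window by design; in the illustration they are the majority.
- *That quality of life goes unanalyzed.* SAP 9.13 also plans treatment comparisons by MCI event status with one value per subject, and SAP 9.9 plans descriptive summaries.

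**Conclusion.** The planned analysis does not match the collection schedule and should be corrected. If SAP 9.9.9 governs 9.13, 55 of the 66 covariance parameters are unidentified and the MMRM becomes a set of unconnected cross-sectional comparisons: mostly withdrawals in early windows, a mix of dropouts and administrative completers near Month 48. The count of 55 is exact given at most one post-baseline value per subject and 11 windows. The Month 48 shares are illustrative, and also require that EoS/EW values be windowed by study day.

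The SAP's own treatment of NPI-Q suggests an oversight rather than a deliberate choice. The consequence is confined to these quality-of-life outcomes. They are outside the testing sequence in SAP 9.9.8, so primary and key secondary conclusions are not affected.

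**What to change.** In SAP 9.13, replace the by-visit MMRM for the EQ-5D index and VAS, the SF-36 component T scores and the SF-36 domain T scores with the ANCOVA already specified for NPI-Q: change from baseline to EoS/EW, with baseline, treatment, center, gender, education and age.

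Two companion edits are needed:

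- State an express exception to the unscheduled-value exclusion in SAP 9.9.9, so that the last CMFV value is used where the EoS/EW assessment was waived under Appendix A footnote (b) or (u). Without it, converters would largely be missing from the ANCOVA.
- Add EQ-5D and SF-36 to SAP Table 9.a, footnote (c).

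The cost is SAP wording and reuse of the NPI-Q code; no new data are required. The downside is a single end-of-study estimate over follow-up that varies between subjects and still depends on how they exit, as already accepted for NPI-Q. The rule in SAP 9.1.3 that drops efficacy data obtained more than 7 days after the last dose could also remove some exit values, so the number of subjects contributing should be reported by arm.
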